Supplementing evidence-based commercial weight management program with inhibitory control training: A pilot study

NCT04747886

STUDY00001164

June 15, 2022

[name]

Cedars-Sinai Research Center

TABLE OF CONTENTS

PROTOCOL Summary.....	3
General Information	3
1.0 BACKGROUND, RATIONALE	3
2.0 STUDY OBJECTIVES	5
3.0 Study Population	6
3.1 Selection of the Study Population	6
3.2 Inclusion Criteria	6
3.3 Exclusion Criteria.....	6
3.4 Subject Screening and Enrollment.....	6
3.5 Subject Recruitment	7
4.0 STUDY DESIGN AND METHODS	7
4.1 Overview of Study Design and Procedures.....	7
4.2 Study Arms	7
4.3 Measurements	7
5.0 DATA COLLECTION and MANAGEMENT	11
5.1 Data Procurement.....	11
5.2 Time Period of data under review	11
5.3 Variables collected	11
5.4 Source documents	12
5.5 Data Collection and Storage	12
5.6 Confidentiality and Security of Data	12
6.0 DATA AND SAFETY MONITORING.....	13
6.1 Data and Safety Monitoring Plan.....	13
6.2 Quality Control and Quality Assurance.....	13
7.0 STATISTICAL CONSIDERATIONS	13
7.1 Study Outcome Measures.....	13
7.2 Sample Considerations	14
7.3 Statistical Analyses.....	14
8.0 REFERENCES.....	15

PROTOCOL SUMMARY

Purpose and Knowledge to be Gained	This two-arm pilot study will be used to estimate the effect size in weight loss of supplementing the WW (formerly Weight Watchers) online program with gamified inhibitory control training (PolyRules!) among adults with overweight or obesity.
Research Procedures	
 Participants (n=30) will be randomly assigned to one of two study arms: (1) WW (formerly weight watchers) only or (2) WW + Gamified inhibitory control training (PolyRules!). All participants will complete demographic, medical history questionnaires and cognitive assessment battery at baseline/enrollment and after completing the 3-month intervention protocol. All interactions with PolyRules! and WW will be passively recorded to monitor frequency of interaction with WW and PolyRules! As compensation for completing all study procedures, participants will receive a \$30 gift card.
Subject Population	
 Adults (aged 18 and over)
Duration	
 12 months

GENERAL INFORMATION

CSMC Co-Investigators	[name] [name]
Biostatistics	[name]
Sponsor/Funder	This study will be Internally funded Institutional Commitment to [name]
Collaborating Institutions Involved in the Research	None

1.0 BACKGROUND, RATIONALE

Evidence-based weight management programs are effective when individuals adhere to treatment recommendations.⁴ However, a majority of individuals are unable to engage and/or sustain a healthy diet⁵⁻⁸ because of the interaction between powerful biological drives and omnipresent obesogenic environmental factors.³¹

A promising framework to address weight management challenges is premised on the reality that environmental cues can never be fully eliminated or prevented, so it may be valuable for

individuals to strengthen their self-regulatory control in order to inhibit their impulses when confronted with temptations. In this view, self-control is like a muscle, and although it fatigues, people can be trained to increase its strength.¹⁻³ This is consistent with [name]^{4,5} and others' findings linking deficits in executive functioning and obesity,⁶⁻¹⁵ and with the use of impulse control training to regulate food-related impulsivity.¹⁶⁻¹⁹ Interventions based on the "Go/No-Go task," a paradigm for studying and training inhibitory control by challenging subjects to withhold impulsive responses, are particularly promising.¹⁸ Go/No-Go training has been shown to increase short-term eating regulation and produce modest weight-loss.^{18,19} However, previous studies include key limitations: limited dosage or training duration, exposure to a small set of stimuli and lack of tailoring to participants' proficiency. Furthermore, Go/No-Go impulse control programs primarily target single processes involved in inhibiting or suppressing motor responses rather than cognitive processes involved in inhibiting cue-response mappings. Resisting food cues not only requires inhibition of impulsive behaviors, but also inhibition of the reinforcing food task set.²⁰ The efficacy of these interventions in improving daily self-regulation is also controversial, with some broad claims based on thin, and often irrelevant, scientific evidence.²¹⁻²⁴

To address the rigor of previous research, we draw upon recent developments in cognitive training with promising functional improvements in several areas (ADHD,²⁵ chemo brain,²⁶ age-related cognitive decline,²⁷ dyslexia,²⁸ schizophrenia,²⁹ sensory deficits,³⁰ brain injury,³¹ in promoting mental fitness²⁷). Novel inhibitory control training (PolyRules!) incorporates stimuli and task structures previously applied in visual perceptual learning and working memory training.^{32,33} PolyRules! adjusts to the users' impulse control proficiency,³⁴⁻³⁶ and gains have been found to generalize to other tasks³⁷⁻⁴⁰ and transfer beyond the training context to complex activities.^{33,41-43} Poly Rules! incorporates four guiding principles of gamification⁴⁴⁻⁴⁷ to reinforce interactions with the app and promote adherence. Gamification, if applied properly, may promote positive behavioral health changes such as weight loss.

In a recent pilot study, we documented the acceptability and feasibility of PolyRules! training among middle-age adults (M age 59±9.4) who were receiving care at Cedars-Sinai Medical Center. We met our enrollment target (n=40) within three hours of emailing the study flyer. This enthusiastic response speaks to the need fulfilled by the proposed lifestyle and cognitive intervention components.

[figure not shown]

Fig 1. Proportion (%) of respondents (n=40) likely or extremely likely to participate if components were offered.

Over 85% of respondents had attempted to lose weight in the last 5 years and 58% had tried to lose weight 5-10+ times. A majority of respondent (79%) said they knew what to eat but struggled keeping a healthy weight and adhering to healthy dietary recommendations. Over 90% of respondents reported that difficulty in resisting tempting foods and self-motivation were barriers to behavior change and weight loss. All components received mean scores >4 (1 = not at all useful, 5 = very useful) in terms of their usefulness in increasing adherence to dietary recommendations (**Figure 1**). All participants

reported they would be likely or extremely likely to participate in an intervention combining inhibitory control training and weight management if it was offered.

A subset of ten participants further completed 10 days of PolyRules! training. All participants completed the daily 30-min training sessions and increased in proficiency over the 10-day training. **Figure 2** illustrates average improvement (••••) in inhibitory control, as well as participants with minimal (ID09) and steep (ID03) gains in performance over the 10 training sessions. Participants described the training as meditative, with the right balance of simplicity in navigating the app and cognitive challenge (e.g., *“I can feel my brain working”*; *“It’s simple but challenging”*; *“Your brain is engaged”*). All participants enjoyed PolyRules! and asked if they could continue using the app. Most frequently cited immediate perceived benefits from using the app were in terms of improved focus, attention and memory (*“I paid more attention than I normally would”*; *“I was able to recall the details about what I read, and this is not how I normally am”*) and in terms of overall thinking and cognition (*“The app is making me smarter!”*; *“I feel more alert”*; *“I’m sharper”*).

This formative work supports the appeal and feasibility of gamified inhibitory control training as a stand-alone component. Additional data is needed to document inhibitory control training in combination to evidence-based weight management program. The proposed two-arm pilot study aims to estimate the effect size in weight loss of supplementing the WW (formerly Weight Watchers) online program with gamified inhibitory control training (PolyRules!) among adults with overweight or obesity. WW is a commercially available structured behavioral weight management program focusing on diet, physical activity and mindset skills. WW was selected for this study because it is the most used commercial program, and the #1 doctor recommended program based on a 2019 survey by Kantar Health of 500 doctors who recommend weight loss programs to patients.⁴⁸⁻⁵²

2.0 STUDY OBJECTIVES

2.1 Primary objective: To estimate the effect size in weight loss of supplementing the WW (formerly Weight Watchers) online program with gamified inhibitory control training (PolyRules!) among adults with overweight or obesity.

2.2 Secondary objectives: To explore whether inhibitory control training confers any benefits in terms of diet quality, physical activity or cognitive functioning in the early stages of a weight management program.

[figure not shown]

Fig 2. Improved inhibitory control over 10-day training.

3.0 STUDY POPULATION

3.1 SELECTION OF THE STUDY POPULATION

Healthy adults (>18 years-old) will be recruited from Cedars-Sinai Medical Center and the general population.

3.3 EXCLUSION CRITERIA

Individuals will not be eligible to participate if they meet any of the following criteria:

- 1) Currently enrolled in weight loss interventions or undergoing bariatric surgery
- 2) Pregnant women
- 3) Individuals with severe cognitive delays or visual/hearing impairment

3.4 SUBJECT SCREENING AND ENROLLMENT

- Study advertisements (flyers, online posting) will instruct interested individuals to contact the study research coordinators via email, phone or text message for more information.
- Individuals who contact the study team will be screened over the phone or provided a REDCap link containing the screening questions. After the screening questions are completed, the study team will review the information and follow up with individuals over the phone, email or via text to inform them if they are eligible for the study and explain the consenting process.
- Electronic consent (eIC) will be obtained using DocuSign. The study coordinator will email the electronic consent to potential participants and then schedule a time to review it over the phone, MS Teams or other video-conferencing software. During this time individuals will have the opportunity to ask questions and discontinue if they are no longer interested in the study. If they want to enroll in the study, the coordinator will email the consent (via DocuSign portal) with the signature fields highlighted to indicate a signature is required. Signature capture can be performed by a stylus and signature pad, mouse, signing with a finger on a touch screen, or by typing a name in an e-signature. When the document is signed electronically DocuSign can send a PDF of the eIC to the study team, which will be reviewed by the

coordinator. Once the eIC is complete, a copy will be emailed to the participants, and it will be stored in a Box folder.

3.5 SUBJECT RECRUITMENT

- Participants will be recruited from Cedars-Sinai and through community outreach with flyers posted around the community and distributed at community events. The study will also be posted online on Craigslist and on Cedars' internal online newsletter, the Bridge. Interested individuals will be instructed to contact the study team via email, phone, or text message for more information.

4.0 STUDY DESIGN AND METHODS

4.1 OVERVIEW OF STUDY DESIGN AND PROCEDURES

Participants (n=30) will be randomly assigned to one of two arms: (1) WW (formerly weight watchers) only or (2) WW + Gamified inhibitory control training (PolyRules!). All participants will complete demographic, medical history questionnaires and cognitive assessment battery at baseline/enrollment and after completing the 3-month intervention protocol. As compensation for completing all study procedures, participants will receive a \$30 gift card.

4.2 STUDY ARMS

WW (all participants; n = 30): All participants will receive pre-loaded computer tablets and 3-month access to the WW digital program. WW is a structured behavioral weight management program that focuses on diet, physical activity and mindset skills. The dietary approach is based on creating an energy deficit diet to produce weight loss while also being attentive to the quality of the calories. Specifically, the WW program assigns SmartPoints values to foods based on calories, sugar, saturated fat and protein. In addition, particular foods are assigned a points value of zero (0) to encourage a healthier eating pattern (e.g. fruits, vegetables, non-fat yogurt, fish). Upon sign-up, an individualized SmartPoints budget consisting of a daily SmartPoints target and weekly SmartPoints allowance is calculated based on height, weight, age and sex. The fitness component assigns FitPoints values to physical activities based on the type, duration, intensity and the participant's body weight. Participants receive 24/7 access to coaches, automatic enrollment in a rewards program based on behaviors, weekly emails motivating lifestyle changes and a closed social network for WW members.

WW + PolyRules! (50% of participants, n = 15): Participants assigned to the WW+ Polyrules arm will receive access to the WW online program (as described above) and to the PolyRules! app for three months. Participants will be trained on how to use PolyRules! via Zoom or Team Meeting platforms. Participants will be asked to engage in daily

cognitive training using the PolyRules! app for three months. They will be instructed to start with 20-min of daily cognitive training and to progressively increase their training time to 30-min. All interactions with PolyRules! will be passively recorded to monitor whether participants engage in cognitive training.

4.3 MEASUREMENTS

Demographics

Participants will complete a questionnaire surveying: date of birth, sex, ethnicity, socioeconomic status (SES: education level, household income, marital status, employment status), household composition (multigenerational, single, married, cohabitating, children) and medical history.

Shared weight, dietary and physical activity data

As part of the WW experience, participants are instructed to track their weight, daily food intake and physical activity via the WW mobile app or online website. As a secondary objective, we will explore weight loss, dietary intake and physical activity over the course of the study and across study arms.

Cognitive Functioning

As a secondary objective, we will explore changes in attention, inhibitory control and working memory over the course of the study across study arms.

Executive Functioning

The Behavior Rating Inventory of Executive Function®- Adult Version (BRIEF-A) is a standardized measure of executive functions or self-regulation in everyday environment. The BRIEF-A assesses nine nonoverlapping theoretically and empirically derived clinical scales: Inhibit, Self-Monitor, Plan/Organize, Shift, Initiate, Task Monitor, Emotional Control, Working Memory, and Organization of Materials. BRIEF-A is available in English and Spanish and can be computer-administered.

Attention and Inhibitory Control Tasks

The *Cancellation Task* is a timed, tablet-based test of selective attention and inhibitory control, akin to D2 (Brickenkamp & Zilmer, 1998). There are two versions that can be used interchangeably: Cancellation Letters and Cancellation Pictures. Cancellation - Letters resembles the D2 in that it consists of similar stimuli: characters “d” and “p” with one to four dashes, arranged either individually or in pairs above or below the letters. For Letters, the participant must scan the items from left to right and select all “d”s with two dashes

(targets). In Cancellation - Pictures, letters are replaced with pictures of dogs and monkeys, some of which are rotated along the vertical axis or are presented upside down. For Pictures, the participant must select the upright dog (tail on the left) and the upside-down monkey (tail on right) separately in single blocks and together in a mixed block.

The *Countermapping* task is a relatively fast and easy task that is appropriate for all age levels, including children. The participant is instructed to tap on one of two green buttons in response to a visual stimulus - a picture of a dog or a monkey. For dogs, the participant must tap on the button that is on the same side of the screen (congruent trial); however, when the participant sees a monkey, they must tap on the button that is on the opposite side (incongruent trial). Note that the visual stimuli appear on the left or on the right interchangeably. On incongruent trials, the participant must inhibit a prepotent response to respond on the same side as the visual stimulus. There are 3 blocks of trials, each preceded by a practice session. The stimuli are presented on the screen until the participant responds, with an upper time limit of 15 seconds. Accuracy is typically very high in this task thus the main dependent measure is reaction time for correct responses on congruent and incongruent trials.

Working Memory Tasks

In the *N-Back* task, participants are presented with a consecutive stream of pictures, and the objective is to tap on the pictures that match those presented *N* items earlier. Higher levels of *N* levels increase WM load and make the task more difficult. All participants complete 1-back (Figure 4), 2-back, and 3-back (in that order). Before each level starts, there is a practice session consisting of 10 trials during which performance feedback is provided. The test phase for each *N*-level consists of 30 trials with 9 targets. Progression to 4-back (and beyond) is allowed if the participant made no more than 2 errors on the previous level. Stimuli are presented for 2500 ms (participant can respond during this period) with an ISI of 500 ms.

In the *Letter-Number task*, participants are presented with a mixed order of letters and numbers, which they must remember and sort them numerically and alphabetically. For example, the sequence 'H8T3K5' would be sorted into '358' and 'HKT'. The mixed orders of letter and numbers ranges from 2 to 15. After a short tutorial, the participant practices the task and must get three out of the five trials correct to proceed to the test. The Letter Number Task is split into two parts: The first is a method of limits to find the participants threshold, whereas the second provides additional trials around that threshold. Characters that could be confused with other letters or numbers are excluded (0, I, O, U, X). Moreover, a given sequence does not include any of the characters in the previous trial and it does not contain consecutive numbers and letters.

Visuo-spatial working memory will be measured with a modified Corsi Tasks, a collection of 4 types of tasks (i.e. classic - blocks, simple, complex, sequencing) that are customizable

where an experimenter can select which task mode, stimulus type, and algorithm they want to use. In all versions of the task, the participant is shown instructions and then practices the task. *Corsi Blocks Classic*: The participant first completes *Corsi Blocks Forward* (tap in same order), followed by *Corsi Blocks Reverse* (tap in reverse order). The Corsi Blocks Forward task is split into two parts: the first is a method of limits to find the participants threshold, whereas the second provides additional trials around that threshold. *Complex Corsi*: Combines Simple Corsi with a secondary sorting task in between each trial. In the sorting task, the participant must drag a dog to a bone or a monkey to a banana. The location of the bone and banana are randomized to prevent mnemonic strategies like chunking.

Exit Interview

Table 1 outlines questions asked during the exit interview across study arms.

Table 1. Interview questions across study arms.		
	WW only	WW + PolyRules!
1. What prompted you to participate in the study?	x	x
2. What are the top 3 things that you liked about WW?	x	x
3. Describe any concerns you had regarding WW?	x	x
4. Can you tell me about some changes (good or bad) you have experiences since you have started WW?	x	x
5. Would you continue using WW if available?	x	x
6. What are the top 3 things that you liked about PolyRules!?		x
7. Describe any concerns you had regarding PolyRules!?		x
8. Do you feel cognitive training helped you with your weight loss?		x
9. Can you tell me about some changes (good or bad) you have experienced since you have started using PolyRules!?		x
10. Would you continue using PolyRules! if available		x
11. Would you be interested in participating in a larger study testing the benefits of combining cognitive training and WW	x	x
12. Is there anything else you would like to share about the study	x	x

Schedule of Procedures

Procedures	Enrollment	Intervention	Post-Intervention
Informed Consent (DocuSign)	X		
Baseline assessment	X		
Randomization	X		
Equipment/software/application set-up and training		X	
Intervention: - WW only group - WW + PolyRules! group		X	
Post-intervention assessment			X
Exit interview			X
Equipment Return			X
Compensation			X

5.0 DATA COLLECTION and MANAGEMENT

5.1 DATA PROCUREMENT

This study utilizes primary data collection. Data will be collected from participants enrolled in the study.

5.2 TIME PERIOD OF DATA UNDER REVIEW

Questionnaire data will be collected at baseline / enrollment and after the 3-month intervention protocol. Frequency of PolyRules! use and interactions with the WW program will be passively recorded on the PolyRules! and WW platforms. Participant data will be included in the analysis if at least three valid days of interactions with the WW program and PolyRules! use (if applicable) are available. De-identified data will be kept for 5 years and then destroyed.

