5.3 VARIABLES COLLECTED

- Demographics: date of birth, sex, ethnicity, socioeconomic status (SES: education level, household income, marital status, employment status), household composition (multigenerational, single, married, cohabitating, children) and medical history

- **Weight, dietary and physical activity data.** Participants' reported/tracked weight, food intake and physical activity data via the WW mobile app or online website.
- Executive functioning as measured by the Behavior Rating Inventory of Executive Function® - Adult Version (BRIEF-A)
- Cognitive functioning: inhibitory control, attention, verbal working memory tasks, visuo-spatial working memory tasks, and working memory capacity tasks

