7.0 STATISTICAL CONSIDERATIONS

7.1 STUDY OUTCOME MEASURES

The primary objective of this study is to estimate the effect size in weight loss of supplementing the WW online program with gamified inhibitory control training (PolyRules!) among adults with overweight or obesity.

As a secondary objective, we will explore changes in dietary intake, physical activity, attention, inhibitory control and working memory over the course of study across study arms.

Primary endpoints

- Weight loss from baseline to 3 months.

Secondary endpoints

- As a secondary objective, we will explore dietary intake, physical activity, attention, inhibitory control and working memory over the course of the study and across study arms. We acknowledge that we are not powered to detect between-group difference on these outcomes. However, inasmuch as participants assigned to the WW only group do not engage in inhibitory control training, we expect no change in attention, inhibitory control and working memory over the course of the study among participants randomized to WW only.
- Qualitative outcomes measures will include participant's satisfaction with WW and PolyRules! (if applicable) and perceived benefits. Perceived satisfaction/dissatisfaction and preferred features of the WW and PolyRules! app will be qualitatively assessed and data obtained in semi-structured interviews will be summarized.

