7.2 SAMPLE CONSIDERATIONS

- Sample size was defined based on available funding such that we expect drop-out over 3 months given the study is longitudinal. Therefore, a sample size of 30 will provide us a reasonable sample size to estimate the effect size.

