7.3 STATISTICAL ANALYSES

Descriptive analysis will be presented with mean \pm standard deviation for quantitative variables, and frequency (percentages) for qualitative variables. A 95% confidence interval for the difference in weight loss between WW and WW + PolyRules! will be calculated. Cognitive test scores (inhibitory control, attention, verbal working memory tasks, visuo-spatial working memory tasks, and working memory capacity tasks), executive function, and physical activity questionnaires will be scored and summarized (Mean and SD) by group and used to inform the design of a larger randomized controlled trial. Calculations will be performed using R-package, version 4.0.⁵³

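### Entry to the analysis depends on app use after randomisation, with an extra PolyRules! condition in one arm only, so the primary weight-loss difference can be biased

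*Combined protocol and SAP*

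**What the plan says.** Section 4.1 sets up the comparison: "Participants (n=30) will be randomly assigned to one of two arms". Section 4.2 puts 15 people in the WW + PolyRules! arm, and only they receive that app. The Schedule of Procedures places randomisation at enrolment and app set-up in the intervention phase.

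The primary endpoint in Section 7.1 is "Weight loss from baseline to 3 months". Weight comes from the WW platform: Section 4.3 says "participants are instructed to track their weight, daily food intake and physical activity via the WW mobile app or online website", and Section 5.3 lists "Participants' reported/tracked weight, food intake and physical activity data via the WW mobile app or online website".

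Section 5.2 first notes that use of both apps is recorded passively. Under its next sentence, a person's data are "included in the analysis if at least three valid days of interactions with the WW program and PolyRules! use (if applicable) are available". It does not define a valid day, give a time window, or say whether three days are needed on each app or in total.

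Section 7.3 gives the primary analysis: "A 95% confidence interval for the difference in weight loss between WW and WW + PolyRules! will be calculated". Sections 7.1 to 7.3 name no as-randomised, per-protocol or sensitivity set and no method for missing weights. Section 7.2 says "we expect drop-out over 3 months given the study is longitudinal" but gives no rate.

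**The concern.** Meeting or failing the rule is decided after assignment, and the two arms face different tests. On the natural reading, three days on each app, a PolyRules!-arm participant with usable WW weights who almost never opens PolyRules! is dropped. A WW-only participant with the same WW use is kept. If days on either app count, the PolyRules! arm has the easier test instead.

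The trial's main product is an estimate of what adding PolyRules! to WW does to weight. Selecting on use changes what is estimated, and the 95% CI does not reflect that. Exclusions also widen an interval that already rests on only 30 people with drop-out expected.

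The documents do not fix the direction. The each-app reading favours PolyRules! only if PolyRules! use goes with greater weight loss. Section 1.0 links adherence to success in weight-management programs, but it describes the evidence for earlier impulse-control training as disputed. Because the readings can move the estimate in opposite directions, leaving the choice open also lets it be made after the data are seen.

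**Working it through.** **The plan's own figure.** The sample size of 30 rests on funding, with no SD, effect size, power or drop-out rate, so it cannot be re-derived. The split 15 + 15 = 30 is consistent.

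**Inputs from the documents.** 15 per arm (Sections 4.1 and 4.2); a 95% CI for the difference (7.3), taken as two-sided.

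**Assumptions, not in the documents.** The number k of 15 PolyRules!-arm participants excluded; the correlation ρ between PolyRules! use and weight loss; normal distributions; no true effect.

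**Step 1: CI half-width in SD units,** t(0.975, n1+n2−2) × √(1/n1 + 1/n2):
- 15 v 15: 2.048 × √(1/15 + 1/15) = 0.748
- 14 v 15: 2.052 × √(1/14 + 1/15) = 0.762
- 12 v 15: 2.060 × √(1/12 + 1/15) = 0.798

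**Step 2: shift on the each-app reading, PolyRules! condition only.** Shift = ρ × m, where m is the mean of the top 15−k expected normal order statistics out of 15. Coverage is from 400,000 simulated trials with a pooled t interval.

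| Dropped | m | ρ = −0.2 | ρ = 0 | ρ = 0.2 | ρ = 0.5 | Coverage at ρ = 0.2 / 0.5 |
|---|---|---|---|---|---|---|
| lowest 1 of 15 | 0.1240 | −0.025 | 0 | +0.025 | +0.062 | 94.8% / 94.5% |
| lowest 3 of 15 | 0.3276 | −0.066 | 0 | +0.066 | +0.164 | 94.6% / 92.7% |

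At ρ = 0 coverage is 95.0%. Relative to the 0.748 half-width, the positive shifts run from 0.0248/0.748 = 3.3% to 0.1638/0.748 = 21.9%.

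**Step 3: adding the WW condition in both arms.** Simulation with 2,000,000 draws per case. Further assumptions: WW use correlates 0.3 with weight loss and 0.3 to 0.7 with PolyRules! use; 1/15 or 2/15 fail the WW condition in each arm; 1/15 or 3/15 fail the PolyRules! condition. Shifts in SD:

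| Reading | ρ = 0.2 to 0.5 | ρ = 0 | ρ = −0.2 |
|---|---|---|---|
| Three days on each app | +0.007 to +0.159 | −0.029 to −0.004 | −0.087 to −0.026 |
| Three days on either app | −0.060 to −0.002 | −0.068 to −0.016 | −0.077 to −0.022 |

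The either-app row stands in for a combined count of days. It assumes that people who pass on PolyRules! use alone have a weight on file, which may often be untrue.

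**Step 4: separate check under other assumptions.** In 100,000 simulated trials, use of each app correlated equally with weight loss and the two kinds of use correlated 0.5. With 6.7% failing the WW condition in both arms and 13.3% failing the PolyRules! condition, the shift is 0.06 SD (correlation 0.3) to 0.10 SD (0.5). With 26.7% failing the PolyRules! condition it is 0.11 to 0.19 SD. Analysing all 30 as randomised, with every weight known, gives no shift beyond simulation error (−0.001 to 0.002 SD).

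**The case against.** The sentence sits in a section about the data period, straight after the one on passive logging, and Section 7.3 does not refer back to it. It may have been meant only as a sufficiency rule for usage logs. That is possible, but the text refers to participant data and the analysis without limit, and no other set exists for the primary estimate. If usage logs were the intent, one sentence would say so.

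The bar is also very low. Section 4.2 asks for daily training over three months ("They will be instructed to start with 20-min of daily cognitive training"), so only near-total non-users fail. All ten people in the earlier PolyRules! pilot completed every session. That was over ten days, so it does not settle three-month use, but it gives no support for 3 of 15 failing. With 1 of 15 dropped, the shift is small and coverage is close to nominal. This stands, and it limits the weight of the point.

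Finally, weights come from WW tracking, so people who barely use WW may have no 3-month weight under any rule. This also stands. The group clearly affected is narrow: PolyRules!-arm participants who keep logging weight in WW but hardly open PolyRules!. They are excluded with no counterpart in the other arm. That this is a pilot with no stated hypothesis test does not remove the problem, because the estimate is what the pilot is for.

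**Conclusion.** The point holds and should be fixed. The wording establishes three things: selection after randomisation, a condition that can bind one arm only, and no alternative analysis set for the primary estimate. It does not establish a material bias. Under the assumptions shown, the shift on the each-app reading runs from slightly negative to under 0.2 SD in favour of PolyRules!, always well inside the CI half-width of about 0.75 SD. It is zero or near zero if few people fail or if use is unrelated to weight loss. The loss of precision is modest: the half-width rises to 0.76 SD at 14 v 15 and 0.80 SD at 12 v 15. Confidence is medium, because both size and direction depend on exclusion rates and correlations that the documents do not give.

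**What to change.** State in Sections 5.2 and 7.3:

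> The primary weight-loss estimate and its 95% CI include all randomised participants in their assigned arm, regardless of WW or PolyRules! use, using every available weight.

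Three additions are needed:
- **Missing weights.** State how participants without a 3-month weight enter the estimate. Without this, the sentence above promises an as-randomised analysis but may deliver a complete-case one.
- **The three-day rule.** Keep it only for describing usage or for a labelled sensitivity analysis.
- **Definitions.** Define a valid day, and say whether three days are needed on each app or combined.

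The cost is a few sentences, with no extra participants, visits or measurements. The estimate may come out smaller because non-users are counted. The main gain is keeping PolyRules!-arm participants who have WW weights but little PolyRules! use. Asking for a weight at the scheduled post-intervention assessment is optional; it would recover some WW non-users but mixes weight sources unless the analysis plans for that.
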